3.6 CRITERIA FOR REMOVAL FROM PROTOCOL THERAPY AND OFF STUDY CRITERIA

3.6.1 Criteria for removal from protocol therapy

Prior to removal from study, effort must be made to have all subjects complete a safety visit approximately 30 days following the last dose of study therapy. Criteria for removal from protocol therapy:

- Unacceptable adverse event(s), unless it is felt by the Principal Investigator to be in the patient's best interests to remain on study in exceptional circumstances, including:
 - o DLT as defined in Section 3.1.1
 - o Persistent (> 14 days) treatment-related grade 2 (non-DLT) adverse events
 - o Grade 3 or higher alemtuzumab allergic (infusion) reaction
 - o Third occurrence of alemtuzumab related grade 3 infection
 - o Third occurrence of alemtuzumab related grade 4 hematologic toxicity
 - o Any grade auto-immune cytopenia
 - o Grade ≥3 VTE during or within four weeks of protocol treatment while on appropriate VTE prophylaxis
- The detection of anti-IL-15 neutralizing antibody serum titer ≥ 500 ng/mL as described in **Appendix E** prior to subsequent treatment cycles.
- Evidence the patient has developed autoimmunity that involves a vital organ (heart, kidney, brain, eye, thyroid or adrenal gland, colon, lung). Patients who develop new auto-antibodies without clinical evidence of end-organ dysfunction will be seen by the appropriate internal medicine subspecialists to assess their risk for developing an autoimmune syndrome.
- Inability to receive all doses of rhIL-15 treatment during treatment weeks 1 and/or 2 for any reason.
- Positive pregnancy test
- Completion of protocol therapy including a 30-day safety visit
- Disease progression

3.6.2 Off-Study Criteria

- Voluntary withdrawal of consent by the patient to participate in the study.
- Patient noncompliance with treatment and instructions from study team.
- Institution of another anticancer treatment. **NOTE:** patients who undergo consolidative stem cell transplant or cellular therapy after achieving a complete or partial response to protocol treatment will continue to be on study and followed for progression-free survival.
- Any new medical or psychiatric condition that, in the opinion of the PI, precludes the safe continuation of the study.
- Completion of follow-up period
- Death

Version Date: 09/24/2021

4 CONCOMITANT MEDICATIONS/MEASURES

All patients will receive the following recommended concomitant pre-medications to lessen the acute side effects associated with alemtuzumab infusions.

4.1 Premedication for Alemtuzumab infusions

- Diphenhydramine (25 to 50 mg) IV or orally and acetaminophen (650 mg) orally 15 to 90 minutes prior to all the infusions.
- The doses of these medications may be tapered down or additional premedications (ibuprofen or other non-steroidal anti-inflammatory drugs [NSAIDs]) or anti-emetics added as needed to lessen the acute side effects.
- Avoid NSAIDs in patients with a platelet count <50,000/mm³
- Patients with more severe or significant post treatment side effects may require institution of other appropriate medications (e.g., steroids, epinephrine or meperidine) as needed.

4.2 PREMEDICATION FOR IL-15

• Acetaminophen 650 mg orally 30 to 60 minutes prior to each IL-15 injection as first line and ibuprofen 400 mg or 600 mg orally depending on reactions with acetaminophen as a premed.

4.3 PROPHYLAXIS FOR VIRUS AND/OR PNEUMOCYSTIS

- Patients will receive empiric anti-viral prophylaxis with acyclovir 400 mg twice daily or equivalent for herpetic prophylaxis.
- Patients will receive empiric prophylaxis for *Pneumocystis jiroveci* pneumonia (PJP) with trimethoprim/sulfamethoxazole double strength (DS) one tablet three days each week. The preferred schedule is Monday, Wednesday, Friday. Patients who have G-6PD deficiency, Grade ≥3 neutropenia lasting more than 3 days, and/or allergy to either component may receive inhaled pentamidine 300 mg once a month or other standard treatments.
- PJP and herpes viral prophylaxis will be continued for a minimum of 2 months after completion of the protocol treatment and the CD4+ count is > 200 cells/microL.

4.4 VENOUS THROMBOEMBOLISM (VTE) PROPHYLAXIS

- Patients will be treated with appropriate anticoagulation prophylaxis for VTE, which may include Enoxaparin, Rivaroxaban, heparin or other anticoagulants (see Section 1.2.5 for rationale).
- If a patient develops grade ≥3 VTE during or within four weeks of protocol treatment despite appropriate prophylaxis, study will be stopped and other patients notified per Section 3.1.2.1.

4.5 PLATELETS AND RBC SUPPORT

• Platelets and RBC support will be given as medically indicated to maintain a hemoglobin > 8gm/dL and to maintain the platelet count at a level of at least 10,000/mm³ (unless there is evidence of bleeding in which case a platelet count of 50,000/mm³ will be maintained. All administered blood products will be irradiated and depleted of leukocytes.

Version Date: 09/24/2021

4.6 Prohibited Medications

Patients are prohibited from receiving the following therapies during treatment on this trial:

- Other therapy for the disease under study not specified in this protocol, unless specifically noted as permitted
- Investigational agents other than rhIL-15 and alemtuzumab
- Radiation therapy NOTE: Radiation therapy to a symptomatic solitary lesion may be allowed at the investigator's discretion.
- Live vaccines within 30 days prior to the first dose of trial treatment and while participating in the trial. Examples of live vaccines include, but are not limited to, the following: measles, mumps, rubella, varicella/zoster, yellow fever, rabies, BCG, and typhoid vaccine.

Patients who, in the assessment by the investigator, require the use of any of the aforementioned treatments for clinical management should be removed from study treatment. Patients may receive other medications that the investigator deems to be medically necessary.

5 BIOSPECIMEN COLLECTION

5.1 CORRELATIVE STUDIES FOR RESEARCH AND SPECIAL STUDIES

At the discretion of the PI the following correlative studies may be performed on patients' PBMCs. Prior to administration of IL-15 on day 8 (week 2 day 1), and on day 12 (week 2 day 5), the last day of IL-15 administration, the PBMCs may be evaluated for their capacity to do antibody-dependent cellular cytotoxicity using the laboratory's standard assay. The reactive agents will be both the patients' PBMCs and the PBMCs depleted of CD4 cells using magnetic B column to yield a population of patients' monocytes, NK and B cells. The targets will be both the ATL cell line 43Tb- as well as patients' CD4 T-cells isolated using Miltenyi magnetic beads.

All research samples will have labels affixed to the tubes by the staff person who obtained the samples. The labels will list the patient's name, date of birth, date and time of the blood draw.

5.1.1 Flow-Cytometry

Flow-Cytometry Studies will be done to assess for absolute numbers, percentages of lymphocyte sets, and T-cell subsets.

All FACS samples will be drawn in 10 mL lavender-top tubes and will be performed for the days listed below **during all treatment cycles.** FACS samples should be drawn before the day's dose of study drug. FACS panels will be performed by the [name] and [name] Laboratories for all time points listed. If the Immunology Section Laboratory ([name]'s Lab) is unable to perform the analysis on the specified days, this assessment maybe omitted or replaced with standard TBNK panel.

• Day 1 Pretreatment:

- Two 10 mL lavender top tubes drawn for cryopreservation, Clinical Support Laboratory, [name], [name], [name], [contact] or [contact].
- One 10 mL lavender top tube will be drawn and sent via routine collection routing to the Immunology Laboratory of the NIH Clinical Center 10/ for CD2, CD3, CD4, CD7, CD8, CD14, CD16, CD20, CD25, CD45RA, CD52, CD56, CD57,

Version Date: 09/24/2021

IL-2R/IL-15R beta (CD122), CD127 (IL-7R alpha), CD194, CD62L, IL-15R alpha.

- **Day 2:** Two 10 mL lavender top tubes will be drawn (+/- one hour) prior to administration of that day's rhIL-15 injection for FACS analysis and sent to the Clinical Support Laboratory for cryopreservation.
- Days 8, 26, 33 and 40: One 10 mL lavender top tube will be drawn with the routine blood draws on days 8 (+ 1 day), 26 (+/- 2 days), 33 (+/- 2 days), and 40 (+/- 2 days). Samples will be sent to the \ Clinical Center Immunology Lab as listed previously. Two 10 mL lavender top tubes will also be drawn for the [name] Lab (NIAID) at the same time and sent as specified above.
- 5.1.2 Inflammatory Markers and Cytokine Analysis
 - All samples will be drawn in 4 mL SST tubes at the times listed below.
 - O Week 1, Day 1 pre-therapy and 4 hours (+/- 15 mins), 8 hours (+/- 30 mins), 12 hours (+/- 30 mins) and 24 hours (+/- two hour) after first IL-15 administration
 - Week 3, Day 1 pre-therapy and 4 hours (+/- 15 min), 8 hours (+/- 30 mins), and 24 hours (+/-two hours) after first administration of alemtuzumab.
 - Samples will be sent via courier to:

Clinical Support Laboratory [name] [name] [name] [contact] or [contact])

5.1.3 Anti-IL-15 Antibodies

- All samples will be drawn in 4 mL SST tubes at the times listed below.
 - o Before first dose of IL-15
 - O Days 12 (+/- 1 day), 26 (+/- 2 days), 33(+/- 2 days), and 40 (+/- 2 days), prior to administration of that day's study drug.
- Samples will be sent via courier to:

Clinical Support Laboratory

[name]

[name]

[name]

[contact] or [contact])

5.1.4 IL-2R alpha and MesoScale Discovery

IL-2R alpha and MesoScale Discovery multiplex proinflammatory cytokines (including interferon gamma, IL-1 beta, TNF-alpha, IL-12, p70, IL-6, IL-10) will be performed.

- All samples will be drawn in 4 mL SST tubes at the times listed below.
 - o Before first dose of IL-15
 - After last dose of s.c. IL-15 (+/- 30 mins)
 - O Week 3, Day 1 pre-therapy and 4 hours (+/- 15 mins), 8 hours (+/- 30 mins), and 24

Version Date: 09/24/2021

hours (+/-two hour) after first administration of alemtuzumab

• Samples will be sent via courier to:

Clinical Support Laboratory [name] [name] [name]

[contact] or [contact]

5.1.5 Special FACS analysis

Special FACS analyses will be performed, including of NK cell and ATL/T-PLL/CTCL populations.

- Samples to be drawn from select patients, (to be determined by Physician PI or AI): up to four 10 mL sodium heparin green-top tubes at the times listed below.
 - At baseline
 - Week 3, Day 1 before the first administration of alemtuzumab
 - o Week 3, Day 2 just prior to the second administration of alemtuzumab
- Samples will be sent to:

[name]. Lymphoid Malignancies Branch [name] [contact]

5.1.6 NK cell exhaustion analysis

PBMCs will be viably frozen for batch processing and analysis for immunophenotypic (via FACS) and functional (via cytotoxicity assays) evidence of NK cell exhaustion.

- Samples to be drawn from select patients (to be determined by Physician PI or AI): up to three 10 mL sodium heparin green-top tubes at the times listed below.
 - o At baseline
 - Week 1, Day 3 before the third administration of IL-15
 - Week 2, Day 1 before the sixth administration of IL-15
- Samples will be picked up by:

[name] [name] [contact] (or designated LYMB staff)

• Samples will be sent via courier to:

Clinical Support Laboratory [name] [name] [name]

[contact] or [contact])

Version Date: 09/24/2021

5.1.7 Adult Patients: Blood Drawing Limits for Research Purposes

The amount of blood that may be drawn from adult patients (i.e., those persons 18 years of age or older) for research purposes shall not exceed 10.5 mL/kg or 550 mL, whichever is smaller, over any eight-week period.

5.2 SAMPLE STORAGE, TRACKING AND DISPOSITION

Samples will be ordered in CRIS and tracked through a Clinical Trial Data Management system. Should a CRIS screen not be available, the CRIS downtime procedures will be followed. Samples will not be sent outside NIH without appropriate approvals and/or agreements, if required.

All specimens obtained in the protocol are used as defined in the protocol. Any specimens that are remaining at the completion of the protocol will be stored in the conditions described below. The study will remain open so long as sample or data analysis continues. Samples from consenting subjects will be stored until they are no longer of scientific value or if a subject withdraws consent for their continued use, at which time they will be destroyed.

If the patient withdraws consent the participant's data will be excluded from future distributions, but data that have already been distributed for approved research use will not be able to be retrieved.

The PI will record any loss or unanticipated destruction of samples as a deviation. Reporting will be per the requirements of section 7.2.

- 5.2.1 Procedures for stored serum specimens in the Clinical Support Laboratory, Leidos Biomedical Research, Inc.:
 - The Clinical Support Laboratory, Leidos Biomedical Research, Inc.-Frederick, processes and cryopreserves samples in support of IRB-approved, NCI clinical trials. The laboratory is CLIA certified for anti-IL 15 and certain cytokine measurements, and all laboratory areas operate under a Quality Assurance Plan with documented Standard Operating Procedures that are reviewed annually. Laboratory personnel are assessed for competency prior to being permitted to work with patient samples. Efforts to ensure protection of patient information include:
 - The laboratory is located in a controlled access building and laboratory doors are kept locked at all times. Visitors to the laboratory are required to be accompanied by laboratory staff at all times.
 - Hard copy records or electronic copies of documents containing patient information are kept in the locked laboratory or other controlled access locations.
 - An electronic database is used to store information related to patient samples processed by the laboratory.
 - The database resides on a dedicated program server that is kept in a central, locked computer facility.
 - The facility is supported by two IT specialists who maintain up to date security features including virus and firewall protection.
 - Program access is limited to specified computers as designated by the laboratory director. Each of these computers has a password restricted login screen.

Version Date: 09/24/2021

• The database sample entry program itself is accessed through a password protected entry screen

- The database program has different levels of access approval to limit unauthorized changes to specimen records and the program maintains a sample history.
- Upon specimen receipt each sample is assigned a unique, sequential laboratory accession ID number. All products generated by the laboratory that will be stored either in the laboratory freezers or at a central repository facility are identified by this accession ID.
- Inventory information will be stored at the vial level and each vial will be labeled with both a sample ID and a vial sequence number.
- Vial labels do not contain any personal identifier information.
- Samples are stored inventoried in locked laboratory freezers and are routinely transferred to the NCI-Frederick repository facilities for long term storage.
- Access to stored clinical samples is restricted. Investigators establish sample collections
 under "Source Codes" and the investigator responsible for the collections, the protocol
 Principal Investigator, specifies who has access to the collection. Specific permissions
 will be required to view, input or withdraw samples from a collection.
- Sample withdrawal requests submitted to approved laboratory staff by anyone other than the repository source code owner are submitted to the source code owner for approval. The repository facility will also notify the Source Code holder of any submitted requests for sample withdrawal.
- It is the responsibility of the Source Code holder (the NCI Principal Investigator) to ensure that samples requested and approved for withdrawal are being used in a manner consistent with IRB approval.
- The Clinical Support Laboratory does perform testing services that may be requested by clinical investigators including, but not limited to, immunophenotyping by flow cytometry and cytokine testing using ELISA or multiplex platforms.
- When requests are submitted by the NCI investigator for shipment of samples outside of the NIH it is the policy of the laboratory to request documentation that a Material Transfer Agreement is in place that covers the specimen transfer. At a minimum, the lab needs confirmation that one has been executed or an exception was granted from an office authorized to make such exceptions, e.g., NCI Technical Transfer Center. The laboratory does not provide patient identifier information as part of the transfer process but may, at the discretion of the NCI investigator, group samples from individual patients when that is critical to the testing process.
- The NCI investigator responsible for the sample collection is responsible for ensuring appropriate approvals and/or agreements, if required, prior to requesting the laboratory to ship samples outside of the NIH.

6 DATA COLLECTION AND EVALUATION

6.1 DATA COLLECTION

6.1.1 Summary

The PI will be responsible for overseeing entry of data into an in-house password protected

Version Date: 09/24/2021

electronic system (C3D) and ensuring data accuracy, consistency and timeliness. The principal investigator, associate investigators/research nurses and/or a contracted data manager will assist with the data management efforts. All data obtained during the conduct of the protocol will be kept in secure network drives or in approved alternative sites that comply with NIH security standards. Primary and final analyzed data will have identifiers so that research data can be attributed to an individual human subject participant.

All AEs, including clinically significant abnormal findings on laboratory evaluations, regardless of severity, will be followed for at least 30 days after the last study drug administration and until return to baseline or stabilization of event.

Document AEs from the first study intervention through 30 days after the last study intervention was administered. Beyond 30 days after the last intervention, only adverse events which are serious and related to the study intervention need to be recorded.

End of study procedures: Data will be stored according to HHS, FDA regulations and NIH Intramural Records Retention Schedule as applicable.

Loss or destruction of data: Should we become aware that a major breach in our plan to protect subject confidentiality and trial data has occurred, this will be reported expeditiously per requirements in section 7.2.1.

6.1.2 Data Collection/Recording Exceptions

6.1.2.1 Abnormal Laboratory Values

An abnormal laboratory value will be considered an AE if the laboratory abnormality is characterized by any of the following:

- Results in discontinuation from the study
- Is associated with clinical signs or symptoms
- Requires treatment or any other therapeutic intervention
- Is associated with death or another serious adverse event, including hospitalization.
- Is judged by the Investigator to be of significant clinical impact
- If any abnormal laboratory result is considered clinically significant, the investigator will provide details about the action taken with respect to the test drug and about the patient's outcome.

6.1.2.2 Data Entry Exceptions

The following data will not be entered into C3D:

- Results of History and Physical (H&P) exams.
- Vital Signs (except Baseline Weight and Height which will be entered).

6.2 DATA SHARING PLANS

6.2.1 Human Data Sharing Plan

What data will be shared?

I will share human data generated in this research for future research as follows:

- X Coded, linked data in an NIH-funded or approved public repository.
- X Coded, linked data in BTRIS (automatic for activities in the Clinical Center)

Version Date: 09/24/2021

X Coded, linked or identified data with approved outside collaborators under appropriate agreements.

How and where will the data be shared?

Data will be shared through:

- X An NIH-funded or approved public repository. Insert name or names: ClinicalTrials.gov.
- \underline{X} BTRIS (automatic for activities in the Clinical Center)
- X Publication and/or public presentations.

When will the data be shared?

X At the time of publication or shortly thereafter.

6.2.2 Genomic Data Sharing Plan

This is not applicable to this study at this time as there are no planned genomic studies.

6.3 RESPONSE CRITERIA

Response and progression will be evaluated in this study using the new international criteria proposed by the revised Response Evaluation Criteria in Solid Tumors (RECIST) guideline (version 1.1)(87). Changes in the largest diameter (unidimensional measurement) of the tumor lesions and the shortest diameter in the case of malignant lymph nodes are used in the RECIST criteria. Separately, patients with cutaneous involvement will have their skin disease evaluated by a dermatologist using the mSWAT tool [Appendix I]. Leukemic cells (Sezary or T-PLL) as percentage of PBMCs will also be assessed and reported separately.

6.3.1 Definitions

Evaluable for toxicity: All patients will be evaluable for toxicity from the time of their first treatment with IL-15.

Evaluable for objective response: Only those patients who have measurable disease present at baseline, have completed the 6 weeks of therapy, and have had their disease re-evaluated will be considered evaluable for response. These patients will have their response classified according to the definitions stated below.

Evaluable Non-Target Disease Response: Patients who have lesions present at baseline that are evaluable but do not meet the definitions of measurable disease, have completed the 6 weeks of therapy, and have had their disease re-evaluated will be considered evaluable for non-target disease. The response assessment is based on the presence, absence, or unequivocal progression of the lesions.

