3.1.2 Dose Escalation

Dose escalation will proceed in cohorts of 3 to 6 patients. Patients will not begin treatment at the next higher dose level until all patients treated at the previous dose level have completed the DLT evaluation window and an assessment of DLT has been completed.

Patients will receive s.c. rhIL-15 for the initial period Monday-Friday week 1 and 2. They will be assigned to a dose level sequentially based on their order of entry into the study. The starting dose will be 0.5 mcg/kg/dose and in the absence of dose-limiting toxicities dose escalation will proceed to evaluate dose levels of 1.0 and 2.0 mcg/kg/dose. This initial part of the treatment will be 14 days in length and will be followed by 4 weeks (13 treatments) of alemtuzumab. Only toxicities occurring in this 6-week period will be considered in determining dose escalation. Dose-limiting toxicities are defined in Section 3.1.1. Dose-escalation rules are indicated in the table in Section 3.1.2. As just noted, the first 6 weeks of rhIL-15 and alemtuzumab treatment will be considered in defining criteria for dose escalation and the maximum tolerated dose (MTD).

Dose escalation will proceed in cohorts of 3–6 patients. The MTD is the dose level at which no more than 1 of up to 6 patients experience DLT during the first 6 weeks of treatment, and the dose below that at which at least 2 (of \leq 6) patients have DLT as a result of the drug. If a patient did not experience DLT and did not finish treatment, he or she will not be evaluable for toxicity and will be replaced in the dose level. An additional 3 patients may be enrolled to compensate for inevaluable patients.

Dose escalation table:

Dose Escalation Schedule				
Dose Level	Dose of IND Agent*			

Version Date: 09/24/2021

Dose Escalation Schedule			
Level 1 0.5 mcg/kg/dose			
Level 2 1 mcg/kg/dose			
Level 3 2 mcg/kg/dose			
* Doses are stated as exact dose in units (e.g., mg/m², mcg/kg, etc.) rather than as a percentage.			

Dose-escalation rules:

Number of Patients with DLT at a Given Dose Level	Escalation Decision Rule			
0 out of 3	Enter up to 3 patients at the next dose level			
≥ 2	Dose escalation will be stopped. This dose level will be declared the maximally administered dose (highest dose administered). Up to three (3) additional patients will be entered at the next lowest dose level if only 3 patients were treated previously at that dose.			

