Patients with acute-subtype ATL deemed by the PI or treating investigator to be at high risk for CNS relapse who have not received CNS prophylaxis as part of their prior treatment may receive prophylaxis in the form of cytarabine 40 mg, methotrexate 15 mg, and hydrocortisone 50 mg administered intrathecally (IT) no earlier than Week 3 and every 6-8 weeks thereafter for up to three doses, and may be given on the same day as alemtuzumab. Cytarabine or methotrexate may be omitted in case of prior intolerance or toxicity attributed to either drug. Platelet counts of ≥70,000 /uL need to be confirmed prior to each administration. If CNS disease is detected by cytology or flow cytometry of cerebrospinal fluid taken during IT drug administration, this will be considered disease progression and the patient will be taken off study. These medications (commercial supplies) will be supplied by the Clinical Center with preparation and administration to follow standard clinical guidelines and requirements.

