10 STATISTICAL CONSIDERATIONS

The primary objective of this trial is to determine the safety, toxicity profile, DLT and MTD of rhIL-15 administered at escalating doses s.c. in combination with alemtuzumab. There are three planned dose levels (0.5, 1, and 2 mcg/kg/dose s.c.) and one dosing strategy (weeks 1 and 2 Monday-Friday). In week three all patients will receive alemtuzumab: 3 mg on day 1, 10 mg on day 2, 30 mg on day 3 and 30 mg on Day 5 of the study. The therapy with alemtuzumab will be continued on weeks 4, 5 and 6 on a 3 x weekly schedule at 30 mg for a total of 4 weeks (13 treatments) of alemtuzumab.

The determination of MTD follows the 3+3 design in which 3 to 6 patients will be enrolled in each combination of dose level. In the initial cohort (Cohort 1), at least 3 patients will be enrolled to receive 0.5 mcg/kg/dose of rhIL-15. In Cohort 2, patients will be enrolled to receive 1 mcg/kg/dose of rhIL-15; and in Cohort 3 patients will receive 2 mcg/kg/dose of IL-15.

The MTD will be based on the assessment of DLT during the first 6 weeks of treatment and will be defined as the dose level at which less than one-third of patients (0/3 or 0-1/6 patients) treated at that dose experience a DLT, with the next higher dose level demonstrating a one-third or greater number of patients (≥2/3 or ≥2/6 patients) having DLT. If a patient did not experience DLT and did not finish the 6 weeks of therapy, this patient will not be evaluable for determination of the MTD and will be replaced in the dose level. An additional 3 to 6 patients will be enrolled at the MTD or, if no severe or dose-limiting toxicities are encountered, the maximum administered dose of rhIL-15, so that a total of 9 patients will be treated at this dose to better characterize the clinical activity of rhIL-15 in this patient population. Accordingly, if all dose levels are evaluated (6 patients per dose level with 9 total patients at the MTD or maximum administered dose) a maximum of 21 evaluable patients will be enrolled. Similarly, if all dose levels are evaluated, the minimum number of evaluable patients required will be 15. An additional 9 patients may be enrolled to compensate for inevaluable patients; thus, bringing the maximum accrual ceiling to 30.

It is expected that accrual can be completed in 60 months.

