Using this dose escalation scheme, the probability of escalating to the next dose level, based on the true rate of DLT at the current dose, is given by the following table (each group will be considered independently of the other):

True toxicity at a given dose	10%	20%	30%	40%	50%	60%
Probability of escalating	.91	.71	.49	.31	.17	.08

The secondary objectives are first to evaluate the potential antitumor activity of the combination of rhIL-15 and alemtuzumab assessing the clinical response rate and time to progression, Another secondary objective is to characterize the biological effects of rhIL-15 administered with alemtuzumab by FACS analysis to define the percentages and absolute numbers of circulating lymphocytes (T and NK cells) and the T-cell subsets naïve, central and effector memory subsets (based on expression of CD52, CD56, CD4, CD8, CD45RO, CD45RA, CD28, CD95, CD194, and CCR7) by flow cytometry. Finally, a secondary objective is to define the effect of the combination on the plasma levels of proinflammatory cytokines using Mesoscale analysis.

Version Date: 09/24/2021

The secondary objectives of the study include characterize the biological effects of rhIL-15 administered with alemtuzumab on the percentages and absolute number of circulating lymphocytes (T and NK cells) and the T-cell subsets naïve, central and effector memory subsets (based on expression of CD52, CD56, CD4, CD8, CD45 RO, CD45RA, CD28, CD95, CCR7, and CD62L) by flow cytometry, and plasma levels of proinflammatory cytokines. Summary statistics will be reported for these measures and considered exploratory.

The accrual ceiling of 24 participants was determined to include the sample size needed for statistical analysis of the safety, toxicity and maximum tolerated dose in this Phase I trial. It provides for 3 inevaluable participants as well as for an expanded cohort of 9 participants at the maximum tolerated dose.

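### Response is classified only in patients who complete 6 weeks of therapy, so early failures leave the denominator and the response rate tends to be biased upward

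*Combined protocol and SAP*

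**What the plan says.** Section 6.3.1 limits the objective-response set by three conditions: "Only those patients who have measurable disease present at baseline, have completed the 6 weeks of therapy, and have had their disease re-evaluated" are evaluable, and it is these patients whose response is then classified. The non-target category covers patients whose lesions "do not meet the definitions of measurable disease, have completed the 6 weeks of therapy, and have had their disease re-evaluated". By contrast, the same section counts every patient for toxicity from the first IL-15 dose.

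Several rules end therapy before week 6:

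- Section 3.3 gives alemtuzumab only while there is no progression or unacceptable toxicity.
- Section 3.6.1 removes patients for progression, for DLT (unless the investigator makes an exception), and for "Inability to receive all doses of rhIL-15 treatment during treatment weeks 1 and/or 2 for any reason".
- Section 3.2 says of CNS disease found at intrathecal dosing, which may start in week 3, that "this will be considered disease progression and the patient will be taken off study".
- Section 3.4.2 restages at the end of weeks 3 and 6, so progression can be documented halfway through.

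On replacement, Section 10 says of a patient who leaves without a DLT that "this patient will not be evaluable for determination of the MTD and will be replaced in the dose level". Section 3.1.2 has the same rule: "he or she will not be evaluable for toxicity and will be replaced in the dose level".

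Response rate is a secondary endpoint (1.1.2), and Section 10 justifies the group of 9 at the MTD or maximum administered dose by the need to describe clinical activity. Section 10 gives no denominator, interval or all-treated set for the response rate.

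**The concern.** Whether a patient completes 6 weeks depends on how treatment goes, and the protocol ties non-completion to failure. A patient whose progression is documented at the week-3 scan normally cannot enter the response set. A patient whose progression is first seen at week 6, after full treatment, does enter it. The two differ only in how fast they failed, and the faster failure is the one removed.

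A rate among completers therefore overstates activity in treated patients if early leavers are mostly non-responders. Replacement makes this harder to see, because the group can still show 9 patients. The comparison with alemtuzumab alone also suffers. The rate of 15 of 29 in Section 1.2.2.4 kept the one patient who was not evaluable for response in its denominator.

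**Working it through.** **1. The plan's own figures.** The plan states no response figure for this trial. Its counts reproduce: 6+6+9 = 21 evaluable at most, 3+3+9 = 15 at least, and 21+9 = 30 as the ceiling. The other ceiling in Section 10 is 21+3 = 24. The earlier ATL trial also reproduces: 15/29 = 51.7%, exact 95% CI 32.5-70.6%. Without the non-evaluable patient it would be 15/28 = 53.6%.

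**2. Who enters the response set under 6.3.1.**

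| Course | Completes 6 weeks | In the response set | Replaced |
|---|---|---|---|
| Progression at week 3, therapy ended | No | No | Yes, if no DLT |
| CNS disease found before week 6 ends | No | No | Yes, if no DLT |
| Missed rhIL-15 doses, therapy ended | No | No | Yes, if no DLT |
| Death before week 6 | No | No | Yes, if no DLT |
| DLT, therapy ended | No | No | No |
| Response at week 3, then early stop | No | No | Yes, if no DLT |
| Full therapy, progression on week-6 scan | Yes | Yes, as non-response | Not applicable |

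All but one of the excluded courses would otherwise count as non-response, barring a documented earlier response. The exception, a week-3 responder who stops, pulls the other way.

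**3. Formula.** Let p be the all-treated response rate, d the share excluded, and f the response rate among those excluded.

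- Completer rate = (p - d·f)/(1 - d)
- Bias = completer rate - p = d(p - f)/(1 - d)

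The bias is upward whenever f < p. With f = 0 the completer rate is p/(1 - d):

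| d | Source of d | 1/(1-d) |
|---|---|---|
| 10% | Assumed | 1.11 |
| 3/24 = 12.5% | Section 10: "It provides for 3 inevaluable participants" | 1.14 |
| 20% | Assumed | 1.25 |
| 9/30 = 30% | Section 10: "An additional 9 patients may be enrolled to compensate for inevaluable patients" | 1.43 |

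The two Section 10 rows assume that the whole allowance is used by non-responding leavers. They are allowances for MTD evaluability, not forecasts, and they come from two ceilings (24 and 30) that do not agree with each other.

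**4. Example for the group of 9.** Assume that all patients have measurable disease and that there are 4 responders. Intervals are exact (Clopper-Pearson) 95%.

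| Situation | Completer rate | All-treated rate |
|---|---|---|
| No leavers | 4/9 = 44.4% (13.7-78.8) | 4/9 = 44.4% |
| 1 replaced non-responder | 4/9 = 44.4% | 4/10 = 40.0% (12.2-73.8) |
| 2 replaced non-responders | 4/9 = 44.4% | 4/11 = 36.4% (10.9-69.2) |
| 3 replaced non-responders | 4/9 = 44.4% | 4/12 = 33.3% (9.9-65.1) |
| 3 replaced, 1 had responded | 4/9 = 44.4% | 5/12 = 41.7% |
| 3 replaced, 2 had responded | 4/9 = 44.4% | 6/12 = 50.0% |
| 1 of 9 stops for DLT, not replaced | 4/8 = 50.0% (15.7-84.3) | 4/9 = 44.4% |

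The last row shows that the bias does not depend on replacement.

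**5. Is early loss plausible?** Section 3.1.2.1 warns of rapid progression and of deaths during salvage treatment in acute ATL. In the earlier trial the median time to treatment failure was 1.6 months and median PFS 2.0 months. Six weeks is 42/30.4375 = 1.38 months. Assuming exponential times, the share failing before then is 1 - exp(-ln2 × 1.38/1.6) = 45% for treatment failure and 1 - exp(-ln2 × 1.38/2.0) = 38% for PFS. This shows only that early failure need not be rare. That trial included lymphomatous ATL, which is excluded here, and this one also enrols PTCL, CTCL and T-PLL.

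**The case against.** The strongest reply has four parts.

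- **The denominator is inferred.** Section 10 describes no response analysis, so no sentence says that the rate will be responders over evaluable patients. This is true, but 6.3.1 is the only rule given, and it says whose response is classified. A report that follows the plan would use completers.
- **Replacement is written for the MTD, not for response.** Also true. Replacement places are optional, and since patients may enter with evaluable disease only, 9 treated patients need not give 9 in the objective-response set. The examples therefore rest on the measurable-disease assumption stated with them. The bias itself comes from 6.3.1, with or without replacement.
- **Section 6.3.4.3 keeps early failures visible.** It records best response from the start of treatment, includes progression as a category and asks that symptomatic deterioration be reported. But it governs how a response is classified, and it does not return excluded patients to the denominator. It sits awkwardly with 6.3.1 and does not repair it.
- **Little depends on the rate.** Response is secondary, with no hypothesis or decision rule, and in the replacement examples with non-responding leavers the shift is 4 to 11 points against an interval of 14-79%. This limits the severity. But the shift is systematic, and the interval does not reflect it.

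A further fair point is that the objective concerns the combination, and a patient who stops during weeks 1 or 2 may never receive alemtuzumab. The fix offers a second set for that reason.

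**Conclusion.** The concern holds. The stated evaluability rule removes early progression, death and early stopping without response from the response denominator, for both measurable and non-target disease, and nothing elsewhere restores them. The direction is upward provided that leavers respond less often than treated patients overall.

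The size cannot be fixed from the documents. The factor is 1.11 to 1.43 if 10% to 30% are excluded and none of them responded, and the bias shrinks or reverses if some had. It affects the reported response rate and its comparison with the earlier trial. It does not affect the MTD, toxicity evaluability under 6.3.1, PFS (6.3.6), or any sample size or error rate. It should be fixed, because response rate is a named endpoint and the remedy is simple.

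**What to change.** In Sections 6.3.1 and 10:

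- Make the main response set all patients with measurable disease at baseline who received at least one dose of rhIL-15, including those later replaced. Optionally also show those who received at least one dose of alemtuzumab.
- Classify each patient by best response from the start of treatment, as in 6.3.4.3, so that a documented week-3 response counts even if therapy stops later.
- Count progression, death or early stopping without a documented response, and absence of any post-baseline assessment, as non-response.
- Report the rate with an exact 95% CI. Keep the 6-week-completer rate as supportive, with the number of leavers and their reasons.
- Remove the completion condition from the non-target category in the same way, and report its categories over all treated patients who have only non-measurable disease.

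The cost is wording only. No new data or patients are needed and no treatment rule changes. The reported rate is likely to be somewhat less favourable.
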